## **7.2 26-Week Visit (T26) (Day 168 to Day 196)**

### **Dental Exam and Treatment**

- Dentists will administer the Safety Questionnaire (Pre-Exam).

- Hygienists will perform dental examination at participant's respective housing facility to evaluate caries arrest and identify new decay.
- Study staff will record results of dental examination.
- Hygienists, under the direction of the study dentist, will administer the intervention treatment (based on study arm) for all previously treated lesions and newly identified active root or coronal carious lesion with ICDAS-II lesion severity code of 3 or greater.
- Study staff will give participants referral sheets with exam results and direction to follow up with their personal dentist for routine dental care.
- If a participant reports any issue with the applied treatment within one week of the treatment date, the study team will return to the housing facility to examine and correct the treated tooth as needed. Within 48 hours, the study team will call the participant to ask the participant if the issue has been resolved and will administer a paper safety questionnaire. The completed paper safety questionnaire will be stored in the CRF folder and documentation of the return visit/treatment will be added to the participant's electronic record.

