## Follow-Up Data Collection

- Study staff will contact participants by phone (within 48 hours of treatment) to complete the safety survey.
- Study staff will interview participants one-on-one at the housing facility to update contact information and enter participant responses to the oral health symptoms, tooth pain/sensitivity, oral health quality of life, *COVID-19 dental visit* and the satisfaction survey.
- Study staff will randomly select 24-30 participants who have completed treatment for three focus group sessions to be held at a housing facility during years two, *three and four*. Participants will be selected from those who have completed treatment and is geared to understanding participant experiences with non-surgical regimens and to identify ways to improve and disseminate in other community-based settings nationally.

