**Secondary outcomes: Older adults' new decay and GOHRQoL (Arm 1: SDF vs. Arm 2: ART +FV) will be assessed through:**

- Clinical dental exam: A newly carious tooth is defined as any tooth receiving an ICDAS lesion code  $\geq 3$  that received a sound code on the previous dental exam or any tooth surface with an ICDAS filling code  $\geq 3$  that previously did not have one. The number of teeth with new decay or filling will be assessed through clinical dental exams ( $T_0$ ,  $T_{26}$ , and  $T_{52}$ ) and recorded on the ICDAS Assessment form.
- Self-reported evaluation: The Geriatric Oral Health-related Quality of Life (GOHRQoL) consist of 12 questions and will be used to assess the impact of the intervention on participants overall oral health quality of life. The overall score will be calculated with higher scores indicating that the participant has greater oral health Quality of Life. The measures will be collected within two week of the baseline visit, the 26-week visit ( $T_0$ ,  $T_{26}$ ), and 52-week visit exam ( $T_{52}$ ).

**Process outcome: Safety and satisfaction and moderating variables (Arm 1: SDF vs. Arm 2: ART +FV) will be assessed through:**

- The Safety Questionnaire-Revised for Adults consists of 15 main adverse events (i.e., existence of dental insurance, severity of adverse symptoms after receiving the dental treatment) and will be used to identify adverse events. Participants will complete this survey pre- and post-exam/treatment at the baseline visit, 26-week visit, and the 52-week visit, respectively. The treatment satisfaction will be assessed through the treatment satisfaction questionnaire for medication (TSQM) modified for Dental and satisfaction with new treatment for cavities, comprised of six questions. The overall average score will be assessed from these two scales with higher mean score indicating better satisfaction with the study treatment. The measures will be conducted during the baseline visit, follow-up visit, and final exam ( $T_0$ ,  $T_{26}$ , and  $T_{52}$ ).

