### 11.2 Sample Size Considerations (RC-3)

For continuous outcomes we computed power using a variance correction (i.e., variance inflation factor) to take into account possible correlations of outcomes within cluster. All computations of required effective samples sizes (or corresponding power) were done using the PASS 2005 software. For binary outcomes, we used a specialized program for cluster randomization (a non-inferiority test comparing two proportions).

The primary outcome tooth pain was defined as change in pain (based on a 100-mm visual analogue pain scale (VAS), where higher is worse pain) from baseline to 1 year. We assume a mean difference of 0 between SDF and ART+FV, and consider non-inferiority to be within a margin (mean difference) of 8 between SDF and ART+FV arms; and based on prior literature also assume a common standard deviation of 25. Further, we assumed an average of 25 subjects recruited per site, an intraclass correlation (ICC) of 0.01 (based on prior studies and literature), and a 15% dropout rate (based on prior studies). The use of a 0.025 alpha-level one-sided t-test to test the null hypothesis of inferiority versus the alternative hypothesis of non-inferiority (as defined above), 11 sites per treatment group (corresponding to 275 subjects per treatment group or 550 total) will provide an estimated 89% power to conclude non-inferiority. Even if the ICC is higher (0.02), there will still be 83% power to detect non-inferiority.

A second primary outcome is arrest rate. Previous data show a high arrest rate (of around 90%) for ART + FV. We expect a similar arrest rate for SDF. For the power calculation we suppose the unit of analysis to be the person, and consider the binary outcome of 'arrest' defined as all lesions for an individual being arrested. We assume equal (person-level) arrest rates of 90% for the ART+FV and SDF groups, and consider non-inferiority to be within a margin (difference in arrest proportions for ART+FV versus SDF) of 0.09. With the same assumptions as before using a 0.025 alpha level one-sided z test, the targeted sample size of 275 subjects in 11 sites per treatment group will provide an estimated 85% power to conclude non-inferiority. For a higher ICC of 0.02, there will still about 80% power to detect non-inferiority.

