Secondarily, we will extend the above GEE approach to analyze the repeated (baseline, 26 and 52-week) measures for each outcome. The models for each outcome will include the same prognostic variables as before, as well as time and a time by treatment interaction. We will allow for correlations among the repeated measures, e.g., using a first-order autocorrelation structure. If a substantial within-facility correlation is found we may need to incorporate facility as a second cluster levels (within which person – the first cluster level – is nested). We will estimate and test (via a robust t-test) the interaction term to compare trends over time for the two interventions. If the use of two cluster levels is not found to be feasible in the GEE approach, we will consider a generalized mixed effects model approach.

**Causal Inference standards (CI-1, CI-2, CI-3, CI-4):** Our use of randomization and adjustment in regression models should be sufficient to provide causally interpretable intervention effect estimates; special causal inference techniques such as propensity score or instrumental variable methods often indicated for observational studies, will therefore not be necessary for our data analysis. We will avoid biases in causal inferences about the intended interventions by using an intent-to-treat approach, in which individuals are analyzed according to randomized groups without regard to (extent of) treatment actually received.

**Sensitivity Analyses IR-5:** We will check sensitivity of conclusions to model assumptions as well as methodological decisions such as outcome definition. In particular, for the arrest outcome, our primary analysis is based on a binary indicator of 'complete' arrest of all lesions for an individual. We will seek to corroborate results from this approach with an alternative approach analyzing

number of lesions arrested. For the GEE analyses, planned for all outcomes, sensitivity will be assessed in part by using alternative working covariance structures and alternative sets of predictors. For some outcomes, alternative distributions will be considered; for example, for number of arrested lesions, possible distributions include Poisson, negative binomial, zero-inflated Poisson (ZIP), and zero-inflated negative binomial (ZINB). Sensitivity to assumptions regarding missing data will also be investigated as described further below.

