### 13.2 Study Intervention and Study Questionnaires

#### **13.2.1 Quality Assurance Procedures**

##### ***Study Staff:***

Study staff who will recruit and interact with participants at the facilities, and document study activities will attend in-person training which will incorporate the topics of human subject protection, Good Clinical Practice (GCP), and adherence to the study protocol. As part of tracking and managing study records, staff members will learn how to document activities that occur with subjects, update study documentation and use the tracking and audit logs. To assess proficiency, the study staff will be certified in the topics presented to ensure their comprehension of the expectations.

In addition, all study staff will be trained to make calls during the dedicated staff training. A script for each type of call will be created in REDCap and study staff will practice during training until they are proficient in utilizing the script and recording the call details.

Additionally, the dental hygienists will undergo calibration exercises prior to the main study to become proficient in exam related study procedures and to maintain intra- and inter-examiner agreement. Dentist experts in the application of SDF, ART, and FV will train and calibrate the dental hygienist and study dentist in the clinical protocol during a two day training session. Additionally, a gold standard examiner will calibrate/train the examiners in the ICDAS protocol in a separate 4-day training session. Detailed clinical and caries assessment training, calibration and reproducibility protocols are in the attached training protocol. Hygienists will not utilize dental radiographs. At the 26-week and 52-week exams, the hygienists will not have access to the results of the baseline examination to avoid detection bias.

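### The new-decay rule in 8.1.1 counts fillings on surfaces already carious at baseline, with a result that depends on arm, and the plan gives no scoring rule for extracted or outside-restored lesions in the primary arrest outcome

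*Combined protocol and SAP*

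**What the plan says.** **Primary arrest outcome.** Section 11.2 will "consider the binary outcome of 'arrest' defined as all lesions for an individual being arrested". Section 11.4 confirms that "our primary analysis is based on a binary indicator of 'complete' arrest of all lesions for an individual" and compares the arms with a 95% confidence interval against a margin of 0.09.

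**New decay (secondary outcome).** Section 8.1.1 has two limbs. A tooth is newly carious if it has a lesion code of 3 or more and was sound at the previous exam. A surface also qualifies if it has a filling code of 3 or more where there was none before. The section adds: "The number of teeth with new decay or filling will be assessed through clinical dental exams".

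**Treatment and examination.** In Arm 2 the cavity is restored with glass ionomer at baseline (4.2). In Arm 1 SDF is painted on and nothing is filled (6.2). Assessments come before treatment at each treatment visit (5.4.2). For masking, "At the 26-week and 52-week exams, the hygienists will not have access to the results of the baseline examination to avoid detection bias" (13.2.1).

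**Outside care.** At week 26, "Study staff will give participants referral sheets with exam results and direction to follow up with their personal dentist for routine dental care" (7.2). A "COVID-19 dental visit" questionnaire is given at week 52 (7.3), but no analysis refers to it.

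**Linkage.** Section 13.2.2 plans longitudinal coding of the exam data after collection, and Figure 15.3.1 lists a treatment log.

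**The concern.** A new-decay count should measure disease on surfaces that were previously free of it. The filling limb asks only whether a filling is new, not whether the surface was already diseased and treated. One arm receives fillings as its treatment and the other does not, so the same clinical history gives different counts by arm. New decay carries its own non-inferiority hypothesis (section 4), so an arm-dependent count bears directly on that comparison.

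The arrest outcome has a different problem. Its rule is missing. Outside care between weeks 26 and 52 is foreseeable, because the study itself directs participants to their own dentist. No section says whether the lesions to be judged are all baseline lesions or only those still present, or how an extracted tooth or outside restoration is scored. A person-level all-or-nothing outcome tested against a 9-point margin is sensitive to that choice, so it should be fixed before outcome data are seen by arm.

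**Working it through.** **1. The new-decay rule applied to a surface with a lesion of code 3 or more and no filling at baseline**

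The first limb cannot apply to this surface, because it was not sound. Assume a restoration receives a filling code of 3 or more; the documents do not list the codes.

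| History of the surface | Arm 1 (SDF) | Arm 2 (ART+FV) |
|---|---|---|
| Study treatment only | Not counted: no filling present | Counted at week 26: the study filling was placed after the baseline exam |
| Outside filling or redo between weeks 26 and 52 | Counted at week 52: filling not there before | Not counted again: filling already charted at week 26 |

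Both rows concern a surface already carious at baseline, so neither event is new decay. The first row inflates the Arm 2 count and the second inflates the Arm 1 count. The documents give no rate for the second, so the net effect cannot be calculated.

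**2. The plan's power for arrest, reproduced**

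Inputs from 11.2: 275 per arm, 25 per site, 15% dropout, ICC 0.01 or 0.02, margin 0.09, "using a 0.025 alpha level one-sided z test". Also: "We assume equal (person-level) arrest rates of 90% for the ART+FV and SDF groups".

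- Completers per site: 25 × 0.85 = 21.25. Completers per arm: 275 × 0.85 = 233.75.
- Effective n = 233.75 / [1 + (21.25 − 1) × ICC], which is 194.4 at ICC 0.01 and 166.4 at ICC 0.02.
- Power = Φ(0.09 / √(2 × 0.9 × 0.1 / n) − 1.96), which is 84.1% (stated 85%) and 78.1% (stated about 80%).

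The stated figures reproduce to within 2 points.

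**3. How much the missing arrest rule could matter (assumed rates, effective n 194.4)**

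Put the truth at the margin, with ART+FV 90% and SDF 81%. Let a share r of truly failing persons be scored as arrested. An affected arm then shows 1 − 0.10(1 − r) for ART+FV or 1 − 0.19(1 − r) for SDF.

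Example with r = 20% in both arms: 0.920 versus 0.848, difference −0.072, standard error 0.0323. The chance of declaring non-inferiority is Φ((−0.072 + 0.09)/0.0323 − 1.96) = 8.0%.

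| r | Both arms | SDF arm only | ART+FV arm only |
|---|---|---|---|
| 0 | 2.5% | 2.5% | 2.5% |
| 10% | 4.5% | 7.9% | 1.2% |
| 20% | 8.0% | 20.4% | 0.5% |
| 30% | 14.1% | 41.8% | 0.2% |

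Now take the opposite rule: outside fillings count as failures in the SDF arm but pass as study fillings in the ART+FV arm. With true rates of 90% in both arms, and 1%, 2%, 3% or 5% of SDF persons affected, power falls from 84.1% to 73.0%, 59.7%, 45.9% or 22.2%.

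If such lesions count as failures in both arms and arrest falls to 88%, 85% or 80% in each, power is 78.0%, 70.0% or 60.2%.

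**The case against.** A reader might infer that failed lesions drop out of the outcome, or look arrested, so that failures are scored as successes. The documents do not support this. Sections 11.2 and 11.4 refer to all of a person's lesions, not to those on remaining teeth, and otherwise are silent. Withholding baseline results from the examiner does not prevent later linkage, since longitudinal coding is planned (13.2.2). The attached training protocol (13.2.1) is not available here and may hold coding rules.

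A reader might also infer that the bias favours non-inferiority. Section 3 of the working shows error rates on both sides of 2.5%, depending on the rule. Nor can it be said that a true deficit of up to 9/(1 − f) points is hidden when a share f of failures is rescored. The decision uses the whole confidence interval, not the point estimate. With true rates of 90% and 79%, non-inferiority is declared 0.6% of the time without misclassification, 2.9% at f = 20% and 4.2% at f = 25%. At a deficit of exactly 9/(1 − f), the observed difference sits on the margin and the chance is 2.5%.

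The assumed shares may also be high. Section 2.1 puts annual dental attendance among Medicare beneficiaries at 26%. Section 4.1 reports that 60% of these residents had few or no visits in over three years. The study itself re-treats at week 26 (7.2), and the week-26 referral is for routine care. For a person to be rescored, every failed lesion must have been dealt with outside.

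Finally, scoring every outside restoration as a failure is not neutral. An SDF-treated cavity changes colour and stays unfilled, so a dentist may fill one that has arrested.

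These points remove any directional claim about arrest and any case for failure by default. They do not touch the new-decay rule, which is written down and gives the results tabulated above. Nor do they supply the missing arrest rule.

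**Conclusion.** The concern holds in two parts of different strength.

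The new-decay rule is a stated rule that gives a wrong result. It counts fillings on surfaces already carious at baseline, and which fillings it counts depends on arm. This follows from 8.1.1 read with 4.2 and 5.4.2, given that the restorations receive a filling code of 3 or more. The size is unknown and the two distortions oppose each other.

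The arrest outcome has a gap, not a demonstrated error. Neither the direction nor the size of any bias can be stated. The range of 4.5 to about 14% for one-sided type I error rests on 10 to 30% of failing persons being scored as arrested in both arms, with the truth exactly at the margin; these are assumptions. They show only that the choice of rule can matter at a 9-point margin.

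**What to change.** **In 8.1.1:** exclude from new decay, in both arms, any filling, study or outside, on a surface that already carried a lesion of ICDAS code 3 or greater at baseline or at the earlier exam where it was treated.

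**In 11.2 and 11.4:**
- Fix the arrest denominator at all baseline-treated lesions.
- Identify them by linking the week-52 chart to the baseline chart and the treatment log at data processing, so that examiners stay masked.
- State one scoring rule for lesions extracted or restored outside the study, identical in both arms.
- Report two sensitivity analyses: such lesions scored as not arrested, and as missing.

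**Cost:** SAP wording and derivation code, with no new visit. The week-52 dental-visit questionnaire may help to identify outside care, but its content is not shown and nothing indicates that it records the tooth or procedure. One downside is that further decay on a surface already treated would no longer enter the new-decay count through its filling; the arrest outcome is the place for it.

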### **6.7 Administration of Intervention**

Arm 1: Topical application of 38% silver diamine solution to ICDAS lesions code 3-6.  
Arm 2: Atraumatic Restoration Treatment (ART) to ICDAS lesions code 3-6, followed by topical fluoride varnish (FV) to all teeth.

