**Table 8.1.1 Quantitative Summary of measures, sources, and timeline (IR-4)**

Variable Type	Measure	Scale	Source	Timeline
Intervention by Study Arms	

• Biannual SDF (Arm 1)

• ART + biannual FV(Arm 2)

			$T_0, T_{26}$
Primary Outcome	Clinical dental exam 

• % freq of arrested surface/teeth

• Caries arrest

• overall score

		

• ICDAS Coronal and Root [Dikmen 2015]

	$T_0, T_{26}, T_{52}$

	Self-reported evaluation 
 
• Tooth pain/sensitivity
 
	
 
• overall score
 
	
 
• PROMIS v.1.0 - Pain Intensity 3a [Modified for Dental]
 
• Dental Discomfort Questionnaire [Modified for Adults from Versloot et al. 2006]
 
	T 0 , T 26 , T 52
Secondary Outcomes	Clinical dental exam 
 
• New decay
 
 Self-reported evaluation 
 
• OH-quality of life
 
	
 
• # freq of new decay teeth
 
• GOHRQoL overall score
 
	
 
• ICDAS Coronal and Root [Dikmen 2015]
 
• Geriatric Oral Health Quality of Life (GOHRQoL) [Atchison and Dolan, 1990]
 
	T 0 , T 26 , T 52 T 0 , T 26 , T 52
Process Outcome	
 
• Safety
 
• Satisfaction
 
	
 
• % freq. adverse event
 
• overall score
 
• overall score
 
	
 
• Safety Questionnaire (Pre- and Post-Exam/Treatment [Adapted for Adults from Milgrom et al. 2018]
 
• Treatment Satisfaction Questionnaire for Medication (TSQM) [Modified for Dental]
 
• Satisfaction with New Treatment for cavities [Modified for Adults from Crystal et al. 2017]
 
	T 0 , T 26 , T 52 T 52 T 52

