### 8.1.1 Quantitative outcomes of interventions

The primary (i.e., caries arrest, tooth pain / sensitivity) and secondary outcomes (i.e., presence of new decay, oral health-related quality of life) measure the effectiveness of the study interventions. The process outcome are to access the safety of the interventions and to ascertain patient satisfaction with the treatment 1 year after the initial treatment.

**Primary outcome: Older adults caries arrest and tooth pain / sensitivity (Arm 1: SDF vs. Arm 2: ART + FV) will be assessed through:**

- Clinical dental exam: will be performed at the two intervention time points (T0, T26) and final time point (T52) by a trained and calibrated dental hygienist according to the International Caries Detection and Assessment System II (ICDAS-II). The exam will be used to identify a change in oral health status between the Baseline visit and the 26-week visit (T0 and T26) as well as the 26-week visit and the 52-week visit (T26 and T52).
- Self-reported evaluation: Scales on tooth pain / sensitivity (PROMIS v.1.0, Health Organization; Dental Discomfort Questionnaire (DDQ)) will be used to measure levels of change in oral pain / sensitivity improvement. Higher scores on the PROMIS and DDQ

indicate increased tooth pain / sensitivity. These measures will be conducted during the baseline visit, 26-week visit, and 52-week visit ( $T_0$ ,  $T_{26}$ , and  $T_{52}$ ).

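### The primary arrest endpoint counts all of a person's lesions without fixing which lesions, and the supporting lesion count has no denominator, so new decay can enter the arrest comparison

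*Combined protocol and SAP*

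**What the plan says.** Section 11.2 takes the person as the unit and defines "the binary outcome of 'arrest' defined as all lesions for an individual being arrested". It then states: "We assume equal (person-level) arrest rates of 90% for the ART+FV and SDF groups". The margin is 0.09 and the stated power is 85%. Section 11.4 carries the same binary outcome forward by reference and repeats it under Sensitivity Analyses. None of these places names a lesion set.

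The lesions under treatment change during follow-up. Section 7.2 has treatment given at 26 weeks "for all previously treated lesions and newly identified active root or coronal carious lesion with ICDAS-II lesion severity code of 3 or greater". At 52 weeks (7.3) arrest and new decay are read at the same examination.

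New decay is a secondary outcome (3.2.2). Section 8.1.1 defines it separately, through a lesion code of 3 or more on a tooth "that received a sound code on the previous dental exam", or through a new filling code. Section 6.7 handles sound teeth differently by arm. Arm 1 is "Topical application of 38% silver diamine solution to ICDAS lesions code 3-6"; Arm 2 is "Atraumatic Restoration Treatment (ART) to ICDAS lesions code 3-6, followed by topical fluoride varnish (FV) to all teeth".

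Section 11.4 plans to corroborate the binary result with the number of arrested lesions, under Poisson, negative binomial or zero-inflated models. No offset or denominator is given. Table 8.1.1 lists a further scale for arrest, a percentage "freq of arrested surface/teeth".

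**The concern.** If lesions found at 26 weeks belong to the set, a person whose baseline lesions are all arrested still fails when one new lesion is not. The primary arrest rate then combines two things: how well the treated lesions were arrested, and how many new lesions appeared. The second is the secondary clinical outcome, and the arms differ by design in what is applied to sound teeth. SDF could miss non-inferiority with the same arrest of baseline lesions as ART+FV.

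The planned corroboration does not resolve this, because it moves the other way. More lesions, whether present at baseline or new, lower the chance that all are arrested but raise the number arrested. At equal arrest per lesion, the raw count favours the arm with more decay. As written it is not a measure of arrest.

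The set also has to be constructed by someone. Examiners do not see baseline findings at follow-up (13.2.1), and linkage across visits is left to longitudinal coding of the examination data (13.2.2), for which the protocol gives no rule. The choice would be made after data collection, on a primary outcome.

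**Working it through.** **Inputs from 11.2.** 275 participants in 11 sites per arm, 25 per site, 15% dropout, ICC 0.01 (alternative 0.02), arrest 0.90 in both arms, margin 0.09, one-sided alpha 0.025.

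**Step 1: reproduce the stated power.**
- Completers per arm: 275 × 0.85 = 233.75, or 21.25 per site.
- Design effect: 1 + 20.25 × 0.01 = 1.2025. Effective n: 233.75 / 1.2025 = 194.4.
- P(conclude NI) = Φ[(pS − pA + 0.09)/SE − 1.96], with SE = √{[pA(1 − pA) + pS(1 − pS)] / 194.4}.
- At 0.90 and 0.90: SE = 0.0304, 0.09/SE = 2.96, power **84.1%** against the stated 85%.
- At ICC 0.02: effective n 166.4, power 78.1% against about 80%.

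The plan's figures stand at their inputs.

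**Step 2: let new lesions count.** These assumptions are not in the documents:
- all baseline lesions are arrested in 0.90 of participants in both arms;
- new lesions by 26 weeks are Poisson with mean μ per person;
- each new lesion is arrested independently with probability q.

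The all-lesions rate is then 0.90 × exp[−(1 − q)μ]. Results at ICC 0.01:

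| μ ART+FV | μ SDF | Rates at q = 0.90 | Difference | P(conclude NI), q = 0.90 | P(conclude NI), q = 0.95 |
|---|---|---|---|---|---|
| 0 | 0 | 0.900 / 0.900 | 0 | 84% | 84% |
| 0.25 | 0.25 | 0.878 / 0.878 | 0 | 77% | 81% |
| 0.10 | 0.20 | 0.891 / 0.882 | −0.009 | 71% | 78% |
| 0.25 | 0.50 | 0.878 / 0.856 | −0.022 | 51% | 68% |

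Equal new decay costs only some power. Unequal new decay moves the difference itself, although arrest of baseline lesions is identical. With no new decay there is no effect. If new lesions nearly always share the result of the baseline lesions (q = 0.98 given baseline arrest), the 0.25 against 0.50 case gives 78%.

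The table counts only lesions found by 26 weeks. A lesion first seen at 52 weeks receives no study treatment at that visit (6.8, 6.11), so counting it would make the person a failure almost by construction.

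**Step 3: the raw count under the same 0.25 against 0.50.** With k baseline lesions per person and the same arrest probability for every lesion in both arms, the ratio of mean arrested lesions (SDF to ART+FV) is (k + 0.50)/(k + 0.25):
- k = 1: 1.50 / 1.25 = **1.20**;
- k = 2: 2.50 / 2.25 = 1.11.

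The binary analysis moves against SDF and the count moves in its favour, with no difference in arrest. Dividing by the number of lesions treated removes this.

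**The case against.** The best reply is that the documents already point to baseline lesions. Arrest and new decay are kept apart throughout: primary against secondary in 3.2, arresting existing untreated caries against preventing new decay in 4.2, and separately named in 7.2 and 7.3. The hypothesis in 11.1 is set at 12 months after treatment, which a lesion first treated at week 26 cannot reach by week 52. This stands as the likelier intention. It remains an inference: the wording of the endpoint is unrestricted and the lesion-count analysis has the same gap.

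The reply is also right on these points:
- Section 8.1.1 describes change between the first two visits "as well as the 26-week visit and the 52-week visit". That says what the examination is used for. It does not define the arrest set and is no evidence for the wider reading.
- Section 11.2 already labels the 90% as person-level, so its unit is not an open question.
- Section 11.4 promises sensitivity checks on outcome definition and gives its count distributions as examples, so an offset is not excluded. Neither statement names a lesion set or a denominator.
- Every figure in Step 2 depends on assumed new-decay rates and on independence between lesions. Section 2.1 says that varnish and SDF both prevent new lesions, so the gap between arms could be small. One value of q for both arms is a further simplification: 4.2 and 6.11 place ART at baseline, while 7.2 has arm treatment given to old and new lesions at 26 weeks. Those passages need reconciling.

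A reader might infer that the gap also inflates false claims of non-inferiority. The documents do not support that. If SDF were truly 9 points worse on baseline lesions (0.81 against 0.90), masking would need more new decay under ART+FV, and the plan gives no reason to expect it. With 0.50 (ART+FV) against 0.25 (SDF) and q = 0.90, the chance of concluding non-inferiority is 9.0% instead of 2.5%. In the direction that varnish to all teeth suggests, 0.25 against 0.50, it is 0.8%. Nor is the 9.0% an error if all lesions are the target, because the true difference is then −0.066, inside the margin.

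**Conclusion.** The point holds as a gap in the definition of a primary outcome, together with a supporting analysis that does not measure arrest. The text leans towards baseline lesions but does not say so, and the literal wording admits new lesions. If they are admitted, the likelier consequence is a loss against SDF: from 84% to 51% (68% at q = 0.95) with new lesions of 0.25 against 0.50, and to 71% (78%) with 0.10 against 0.20. These figures illustrate sensitivity; the documents contain no new-decay rates from which to predict the size.

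The problem with the raw count does not depend on those rates. Whatever the rates, the count rises with the number of lesions a person has. The stated 85% power is not in question, and no inflation of the type I error is claimed.

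**What to change.** Before outcomes are analysed by arm:

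1. In 11.2 and 11.4, define the primary arrest set as the lesions treated at baseline (ICDAS 3 or greater), scored at 52 weeks. Count lesions first found at 26 or 52 weeks only as new decay. Report the all-lesions version as a sensitivity analysis.
2. Replace the raw number of arrested lesions with arrested lesions out of baseline-treated lesions, as a binomial outcome or as a count with the log number of treated lesions as offset, in the facility-level GEE already planned.
3. Make the arrest entry in Table 8.1.1 match.

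Keep the 0.09 margin, the confidence-interval rule and the power statement.

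The cost is a derivation rule and analysis code. The examinations at 0, 26 and 52 weeks and the treatment log are already collected, so no participants or visits are added. There are two downsides: lesions must be matched by tooth surface across visits, and the primary result no longer covers lesions first treated at 26 weeks.
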